3.1 Primary, secondary and exploratory objectives and estimands

3.1.1 Primary objective

To demonstrate superiority of three dose levels of oral NNC0385-0434 versus placebo on percent change in LDL-C from baseline to week 12 in patients with established ASCVD or ASCVD risk on maximally tolerated statin dose and other lipid-lowering therapy requiring further LDL-C reduction.

3.1.2 Secondary objectives

To compare the effect on lipid/lipoprotein parameters excluding LDL-C of three dose levels of oral NNC0385-0434 versus placebo in patients with established ASCVD or ASCVD risk on maximally tolerated statin dose and other lipid-lowering therapy requiring further LDL-C reduction.

To compare the effect on lipid/lipoprotein parameters of three dose levels of oral NNC0385-0434 versus s.c. evolocumab in patients with established ASCVD or ASCVD risk on maximally tolerated statin dose and other lipid-lowering therapy requiring further LDL-C reduction.

To compare the safety and tolerability of three dose levels of oral NNC0385-0434 versus placebo in patients with established ASCVD or ASCVD risk on maximally tolerated statin dose and other lipid-lowering therapy requiring further LDL-C reduction.

3.1.3 Exploratory objectives

To examine the population pharmacokinetic and immunogenic properties of three dose levels of oral NNC0385-0434 in patients with established ASCVD or ASCVD risk on maximally tolerated statin dose and other lipid-lowering therapy requiring further LDL-C reduction.

PK sub-study

To assess and compare the pharmacokinetic properties of three dose levels of oral NNC0385-0434 at steady-state between Japanese and non-Japanese patients with established ASCVD or ASCVD risk on maximally tolerated statin dose and other lipid-lowering therapy requiring further LDL-C reduction.

3.1.4 Estimands

For the primary objective, an estimand of primary interest and an additional estimand is defined. The estimands are used to address the trial objectives in terms of two different aspects of the treatment effect of three dose levels of oral NNC0385-0434. A single intercurrent event is considered: Premature treatment discontinuation. Intercurrent events are events occurring after treatment initiation that affect the interpretation, or the existence of the measurements associated with the question of interest.

The primary estimand will be used to address the primary objective and similar estimands will be used to address the secondary objectives for the corresponding supportive secondary endpoints. The additional estimand will be used to address the primary objective for the primary endpoint. The estimands are described below and the attributes of the estimands are presented in [Table 3-1](#).

Primary estimand

The primary estimand addresses the main question of interest: What is the efficacy of three dose levels of oral NNC0385-0434 versus placebo on percent change in LDL-C from baseline to week 12 in patients with established ASCVD or ASCVD risk on maximally tolerated statin dose and other lipid-lowering therapy if all patients had remained on trial treatment? A hypothetical strategy is applied for the intercurrent event premature trial treatment discontinuation. The population-level summary is difference in means.

Results based on the primary estimand quantifies the achievable treatment effect if all patients remain on the trial treatment.

Additional estimand

The additional estimand addresses an additional question of interest: What is the efficacy of three dose levels of oral NNC0385-0434 versus placebo on percent change in LDL-C from baseline to week 12 in patients with established ASCVD or ASCVD risk on maximally tolerated statin dose and other lipid-lowering therapy regardless of premature treatment discontinuation? For this estimand, the treatment policy strategy is applied for the intercurrent event premature trial treatment discontinuation. The population-level summary is difference in means.

Results based on the additional estimand are expected to mirror the clinical practice scenario because the estimand considers both the efficacy and tolerability of oral NNC0385-0434.

Table 3-1 Estimand attributes

Estimand category	Treatment condition	Variable / endpoint	Population of interest	Intercurrent events and strategy	Population-level summary measure
Primary	The effect of three dose levels of oral NNC0385-0434 versus placebo, both in combination with maximally tolerated statin dose and other lipid-lowering therapy.	Change in LDL-cholesterol (%) from baseline to week 12	Patients with established ASCVD or ASCVD risk. Further details can be found in Section 5 .	Hypothetical strategy is applied for the intercurrent event 'premature trial treatment discontinuation'	Difference in means
Additional	The effect of three dose levels of NNC0385-0434 versus placebo, both in combination with maximally tolerated statin dose and other lipid-lowering therapy.			Treatment policy strategy is applied for the intercurrent event 'premature trial treatment discontinuation'	

3.2 Primary, secondary and exploratory endpoints

3.2.1 Primary endpoint

Endpoint title	Time frame	Unit
Change in LDL-cholesterol	From baseline (week 0) to visit 9 (week 12)	%

3.2.2 Secondary endpoints

3.2.2.1 Confirmatory secondary endpoints

Not applicable.

3.2.2.2 Supportive secondary endpoints

Endpoint title	Time frame	Unit
Change in total cholesterol	From baseline (week 0) to visit 9 (week 12)	%
Change in HDL-cholesterol	From baseline (week 0) to visit 9 (week 12)	%
Change in VLDL-cholesterol	From baseline (week 0) to visit 9 (week 12)	%
Change in triglycerides	From baseline (week 0) to visit 9 (week 12)	%
Change in total Apo B	From baseline (week 0) to visit 9 (week 12)	%
Change in total Apo CIII	From baseline (week 0) to visit 9 (week 12)	%
Change in total Lp(a)	From baseline (week 0) to visit 9 (week 12)	Ratio
Treatment-emergent adverse events	From baseline (week 0) to visit 10 (19 weeks + 4 days)	Number of events

3.2.3 Exploratory endpoints

Endpoint title	Time frame	Unit
Concentration of NNC0385-0434 at steady state	From visit 7 (week 6) to visit 9 (week 12)	nmol/L
Occurrence of NNC0385-0434 binding antibodies	From baseline (week 0) to visit 10 (19 weeks + 4 days)	Yes/no
Occurrence of NNC0385-0434 binding antibodies cross reacting with endogenous counterpart (EGF-A)	From baseline (week 0) to visit 10 (19 weeks + 4 days)	Yes/no
Titre of NNC0385-0434 binding antibodies	From baseline (week 0) to visit 10 (19 weeks + 4 days)	No unit

[figure not shown]
PK sub-study		
Endpoint title	Time frame	Unit
AUC _{0-24h,SS} (area under the steady state plasma NNC0385-0434 concentration–time curve)	From 0 to 24 hours after end of treatment at visit 9 (week 12)	h*nmol/L
AUC _{0-∞,SS} (area under the steady state plasma NNC0385-0434 concentration–time curve)	From 0 hours to infinity after end of treatment at visit 9 (week 12)	h*nmol/L
C _{max,SS} (maximum observed plasma NNC0385-0434 concentration at steady state)	From 0 to 24 hours after end of treatment at visit 9 (week 12)	nmol/L
t _{max,SS} (time to maximum observed plasma NNC0385-0434 concentration at steady state)	From 0 to 24 hours after end of treatment at visit 9 (week 12)	Hours
t _{1/2,SS} (terminal phase elimination half-life of NNC0385-0434 at steady state)	After end of treatment at visit 9 (week 12)	Hours

4 Trial design

4.1 Overall design

This is a randomised, multicentre, multinational, seven-armed, parallel group, dose finding trial ([Figure 4-1](#)). The trial will be double-blinded within dose level of oral NNC0385-0434 and size-matched placebo arm. The s.c. evolocumab arm will be open label. The trial population includes patients with established ASCVD or ASCVD risk on maximally tolerated statin dose and other lipid-lowering therapy requiring further LDL-C reduction.

Figure 4-1 Schematic overview of the trial design

Notes: *placebo tablets are sized match to the active arm within dose level. Placebo arms will be pooled in the statistical analyses.

Abbreviations: N: number of patients; OD: Once daily; Q2W: every 2 weeks; s.c. subcutaneous.

The trial includes a 2-week screening period followed by a 12-week treatment period. Additional PK sampling will be performed for 60 patients following the 12 weeks of treatment (referred as 'PK sub-study', see [Section 4.1.1](#)). The follow-up period for all patients is 7 weeks and 4 days. The total duration for each patient will be approximately 22 weeks. Throughout this protocol, the 'main trial' refers to the trial part without PK sub-study sampling.

Oral treatment arms (NNC0385-0434 or placebo) will be administered once daily. Each oral NNC0385-0434 treatment arm will be administered as tablets with varying sizes, but is blinded towards placebo with matching tablet sizes. The s.c. evolocumab treatment arm will be administered every 2 weeks.

The 7 treatment arms consist of 4 active treatment arms and 3 placebo arms, as follows:

- 15 mg NNC0385-0434 co-formulated with 500 mg SNAC tablet once daily (51 patients)
- 40 mg NNC0385-0434 co-formulated with 500 mg SNAC tablet once daily (51 patients)
- 100 mg NNC0385-0434 co-formulated with 500 mg SNAC tablet once daily (51 patients)
- 140 mg evolocumab s.c. injections every 2 weeks (51 patients)
- 3 placebo arms: placebo administered as tablets (without SNAC) once daily (17 patients in each placebo arm, 51 patients in total)

Patients will be randomised 3:1:3:1:3:1:3 according to [Figure 4-1](#). Randomisation will be stratified according to participation in the PK sub-study (yes/no), country (Japan/non-Japan) and population (inclusion criteria 3a/3b). Within each stratum, each patient will be randomly allocated to one of the treatment arms (Section [6.3.1](#)). For the main statistical analyses, the 3 placebo arms will be pooled into one placebo group.

The initial 15 patients (3 patients in each active treatment arm and 1 patient in each of the placebo arms) will be recruited from few pre-selected sites and treated for minimum 4 weeks before recruitment of the remaining 240 patients. Randomisation of the remaining patients will be initiated following medical monitoring of 4 week data of these 15 patients without identification of safety concerns, in addition to review of PK data from the 15 patients 2 weeks after dosing. Specifically, for Japanese patients, an evaluation of the safety and PK from the Japanese PK trial (NN6435-4748) will be performed before randomisation of Japanese patients into the current trial. The safety evaluation will include 12 healthy male Japanese subjects on a 10-day treatment with 15 mg, 40 mg or 100 mg oral NNC0385-0434, or placebo (3 subjects on each). The PK review will include data of the 15 mg and 40 mg cohorts.

Details on risk-based monitoring including medical monitoring and early PK evaluation is provided in Section [10.1.8.2](#).

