4.2 Scientific rationale for trial design

To allow evaluation of dose-response relationship of oral NNC0385-0434, a parallel randomised, double-blinded within dose level, controlled design has been chosen. To minimize bias in the assessment, the oral NNC0385-0434 treatment arms are double-blinded for each dose level of oral NNC0385-0434 with size-matched placebo arm. Three dose levels of NNC0385-0434, covering the expected range for clinically adequate LDL-C lowering, have been chosen to evaluate the dose-response relationship.

The rationale for including a s.c. evolocumab arm is to compare the efficacy of oral NNC0385-0434 against one of the already marketed PCSK9 inhibitors. The s.c. evolocumab arm is open-label to limit unnecessary injections (e.g., by use of double-dummy) as the primary aim of the trial is to investigate the effects of oral NNC0385-0434.

The trial population will consist of patients with established ASCVD or ASCVD risk on maximally tolerated statin dose and other lipid-lowering therapy requiring further LDL-C lowering. In alignment with the European ESC/EAS treatment guideline^{4,5}, this is the target population that will benefit of obtaining LDL-C < 1.8 mmol/L (<70 mg/dL) in order to reduce their ASCVD risk. Specific LDL-C inclusion criteria have been defined for Japanese patients according to the Japanese guidelines for prevention of ASCVD (JAS guidelines)⁶.

The treatment period is set to 12 weeks. The steady state exposure is expected to be reached at approximately 6 weeks into the trial and therefore the complete LDL-C lowering response should be observed within 12 weeks of treatment.

As a precautionary measure, 15 patients will be recruited initially before recruitment of the remaining 240 patients. Medical monitoring of minimum 4 week safety data for these 15 patients will be completed before dosing of the remaining 240 patients in the trial (see Section [10.1.8.2](#)).

PK sub-study

The rationale for including the PK sub-study is to assess and compare the steady state PK profiles of multiple doses of oral NNC0385-0434 in Japanese and non-Japanese patients. Therefore, PK assessments from the evolocumab arm are not relevant and this arm is not included in the PK sub-study.

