6.3 Measures to minimise bias: Randomisation and blinding

6.3.1 Randomisation

- This is a randomised, placebo-controlled trial.
- Patients will be randomised 3:1:3:1:3:1:3 according to [Figure 4-1](#)
- For the PK sub-study:
 - All Japanese patients will be included in the PK sub-study. Once 30 Japanese patients have been included in the PK sub-study and randomised to treatment, any Japanese patient ongoing screening procedures should be considered a screen failure (Section [5.4](#)).
 - Selected non-Japanese sites will include 30 non-Japanese patients for the PK sub-study. Once 30 non-Japanese patients have been randomised to the PK sub-study, eligible non-Japanese patients will be randomised to the main study.
- Randomisation will be stratified according to participation in the PK sub-study (yes/no), country (Japan/non-Japan) and population (inclusion criteria 3a/3b). Within each stratum, each patient will be randomly allocated to one of the treatment arms.
- All patients will be screened and randomised centrally using IWRs and assigned to the next available treatment according to randomisation schedule. Trial product will be dispensed/allocated at the trial visits summarised in the flowchart ([Table 1-1](#)).
- At screening, each patient will be assigned a unique 6-digit number which will remain the same throughout the trial. Each site is assigned a 3-digit number and all patient numbers will start with the site number.

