7.2.1 Replacement of subjects

Patients who discontinue trial product or withdraw from trial will not be replaced.

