10.1.8.2 Monitoring

- The investigator must permit trial-related monitoring, audits, IRB/IEC review, and regulatory agency inspections and provide direct access to source data documents (original documents, data and records). Direct access includes permission to examine, analyse, verify and reproduce any record(s) and report(s) that are important to the evaluation of the trial. If the electronic medical record does not have a visible audit trail, the investigator must provide the monitor with signed and dated printouts. In addition, the relevant site staff should be available for discussions at monitoring visits and between monitoring visits (e.g. by telephone).
- Trial monitors will perform ongoing source data verification to confirm that data entered into the CRF by authorised site personnel are accurate, complete and verifiable from source documents; that the safety and rights of patients are being protected, to monitor drug accountability and collect completed paper CRF pages, if applicable, and that the trial is being conducted in accordance with the currently approved protocol and any other trial agreements, ICH GCP, and all applicable regulatory requirements.
- Monitoring will be conducted using a risk-based approach including risk assessment, monitoring plans, centralised monitoring (remote assessment of data by Novo Nordisk) and visits to sites.
- Monitors will review the patient's medical records and other source data to ensure consistency and/or identify omissions compared to the CRF.

Medical monitoring and early PK evaluation

Bi-weekly medical monitoring of safety data including AEs, vital signs, ECG, and laboratory safety parameters will be performed according to the medical monitoring plan.

The centralised monitoring will include early PK evaluation to ensure that the PK parameters after oral dosing are in the expected range. The early PK evaluation will be performed at 3 early timepoints during the trial and will include all available blinded accumulated plasma concentration data from patients that have initiated treatment. PK data will be related to treatment arm. The early

PK evaluation will be based on nominal time points for the dose administration and PK sampling. Additional PK evaluations may be added if deemed necessary.

- Timepoint 1: After PK data is available from visit 4 (2 weeks of dosing) for the initial 15 patients.
- Timepoint 2: After PK data is available from visit 7 (6 weeks after dosing) for the initial 15 patients

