- Timepoint 3: After PK data is available from visit 8 (9 weeks after dosing) for the initial 15 patients and from visit 4 (2 weeks of dosing) for the following 20 patients.

Further details are described in the interim modelling analysis plan.

The Novo Nordisk NN6435 Safety Committee will be informed immediately in case any of the following criteria are met:

- if the exposure of NNC0385-0434 exceeds the NOAEL exposure observed in the 13-week non-clinical toxicity study (12 mg/kg/day s.c. + 50 mg/kg/day orally)
- if the geometric mean C_{max} of NNC0385-0434 for patients treated with any dose arm of NNC0385-0434 is numerically higher than the geometric mean C_{max} observed in the FHD trial NN64334-4493 (11,015.5 nmol/L).

The initial 15 patients (3 patients in each active treatment arm and 1 patient in each of the placebo arms) will be recruited and treated for minimum 4 weeks before recruitment of the remaining 240 patients. Recruitment of the remaining patients will be initiated following medical monitoring of 4 week data of these 15 patients without identification of safety concerns, in addition to review of PK data from the 15 patients 2 weeks after dosing

If unexpected safety findings occur, a Novo Nordisk Safety Committee will be informed immediately and will take appropriate actions to the information received.

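### Does the stratified randomisation put at risk the stated split of the first 15 patients (3 per active arm, 1 per placebo arm)?

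*Protocol*

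**What the plan says.** Protocol 4.1 and 10.1.8.2 both give the make-up of the first cohort in the same words: "The initial 15 patients (3 patients in each active treatment arm and 1 patient in each of the placebo arms"). Both then hold back the rest of the trial until there has been "medical monitoring of 4 week data of these 15 patients without identification of safety concerns", together with a review of the 2-week PK data. Section 4.2 gives the reason: "As a precautionary measure, 15 patients will be recruited initially before recruitment of the remaining 240 patients". It gives only the total, but refers the reader to 10.1.8.2 for the detail.

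The allocation rule is in 6.3.1. The ratio is "Patients will be randomised 3:1:3:1:3:1:3 according to" the design figure. The strata are: "Randomisation will be stratified according to participation in the PK sub-study (yes/no), country (Japan/non-Japan) and population (inclusion criteria 3a/3b"). The rule is then "Within each stratum, each patient will be randomly allocated to one of the treatment arms". Patients are randomised centrally through the IWRS and take the next available treatment on a schedule that is not reproduced. Neither document gives a block size, an arm cap or a separate list for the first cohort.

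Two other statements bear on the point. In 7.2.1: "Patients who discontinue trial product or withdraw from trial will not be replaced". In 10.1.8.2, on the early PK evaluation: "PK data will be related to treatment arm".

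**The concern.** Two parts of the protocol seem to rest on different mechanisms. The first cohort has an exact composition, stated as fact. The only randomisation described works separately within strata formed by PK sub-study, country and inclusion criterion 3a/3b. Recruiting the cohort from a few pre-selected sites does not put everyone in one stratum, because 3a/3b is a characteristic of the patient. Once the 15 patients fall in two or more strata, each stratum draws from its own sequence and the totals by arm become a matter of chance.

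The cohort's purpose would be at stake. It is there so that each oral dose has been seen in 3 patients for 4 weeks, with PK at 2 weeks, before 240 more patients enter. The other human data on oral dosing in the protocol are a 10-day trial in healthy Japanese men with 3 subjects per dose, so the count at each dose seems to matter. One PK trigger in 10.1.8.2 is a geometric mean for a dose arm, and at the first evaluation that mean would rest on very few patients. The hold is worded on the 15 patients, those who discontinue are not replaced, and the protocol does not say what applies if an arm falls short.

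**Working it through.** **The stated figure.** The ratio 3:1:3:1:3:1:3 (6.3.1) sums to 15. Expected counts are N × r/15:

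- N = 15: 3 per active arm and 1 per placebo arm, as stated in 4.1.
- N = 255: 51 and 17, as stated in 4.1.
- N = 240: 48 and 16.

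The split therefore reproduces as an expected count. The question is whether it also holds exactly.

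**Assumptions.** The documents do not name permuted blocks, a block size or the share of patients in each stratum. The figures below assume permuted blocks within strata, each stratum starting a fresh block, and no cohort list or other IWRS control. The stratum splits are illustrative.

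**One stratum.**

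- Block of 15: the first 15 patients use exactly one block, so P(exact split) = 1. No smaller block has whole numbers in this ratio.
- Block of 30: P = C(6,3)⁴ × C(2,1)³ / C(30,15) = 20⁴ × 2³ / 155,117,520 = 1,280,000 / 155,117,520 = 0.0083.

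**Two strata, blocks of 15, patients divided 14/1.** The block of 14 leaves out one allocation, and the single patient must receive that arm:

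P(exact) = Σ(r/15)² = (4 × 9 + 3 × 1)/225 = 39/225 = 0.173.

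The 100 mg arm has 2 patients if the omitted allocation is 100 mg and the single patient gets another arm: (3/15) × (12/15) = 0.16. At this split it cannot have fewer than 2.

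**Other divisions.** The first s patients of a block follow a multivariate hypergeometric distribution. The distributions for s and 15 − s are convolved and the counts added by arm:

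| | 14/1 | 12/3 | 8/7 |
|---|---|---|---|
| Exact stated split | 17.3% | 2.7% | 0.7% |
| At least one oral dose with 2 or fewer | 48% | 71% | 77% |
| 100 mg with 2 or fewer | 16% | 29% | 33% |
| 100 mg with 0 or 1 | 0% | 4.0% | 8.8% |
| 100 mg with none | 0% | 0.1% | 0.95% |
| Every oral dose with at least 2 | 100% | 88% | 74% |
| Every oral dose with at least 1 | 100% | 99.7% | 97% |
| At least one placebo arm empty | 19% | 43% | 60% |
| No placebo patient at all | 0% | 0.1% | 0.95% |

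**Over the unknown 3a/3b mix.** Let a share q of patients be in the larger of two strata, and weight the exact-split probabilities by the binomial(15, q) distribution of the division. For q = 70%, 80%, 90% and 95%, the stated split occurs in 2.8%, 8.3%, 28.5% and 53.5% of cases.

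**The two readings of the text.**

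1. *The split is binding.* Sections 4.1 and 10.1.8.2 give the composition first and then hold the trial on those same 15 patients. The per-arm count is thus part of what the hold refers to. The schedule has to be built to deliver it, for example with a list for the first cohort, and 6.3.1 excludes nothing of the kind.
2. *The split is nominal.* It is then the ratio applied to 15, as 51 and 17 are the ratio applied to 255. The 18 + 18 patients exposed to NNC0385-0434 in the PK sub-study (4.1.1) come about in the same way: 30 × 9/15 = 18 in each group. Stratified allocation contradicts none of these.

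Neither reading gives a contradiction that has to be resolved.

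**The case for a change.** The strongest case for a change is that the arithmetic is right and the remedy cheap. The protocol states a split and describes a mechanism that, taken alone, secures it under one condition only. Even with 95% of patients in one stratum, the exact split would be little better than a coin toss. One sentence and one IWRS list, with no extra patients, would settle it. The hold is also described variously as a hold on randomisation (4.1), dosing (4.2) and recruitment (10.1.8.2), which makes tidier wording attractive.

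The logic stands: under the stated assumptions the split is not secured by 6.3.1 as written, and the protocol is silent on how it is secured. What does not follow is that the design is at fault. The probabilities assume that the unseen schedule makes no provision for the first cohort, and block details may be left out of a protocol on purpose. Silence on a shortfall is likewise silence in the protocol only: 10.1.8.2 refers to a medical monitoring plan and an interim modelling analysis plan, neither of which is available here.

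The most striking figures carry less weight than they seem to. Empty placebo arms matter little for a review of drug safety and exposure: the three arms are pooled in the main analyses, and the 15 mg and 40 mg arms share one placebo product (6.1). Nothing shows that 2 patients instead of 3 on a dose would alter a review that has no numerical decision rule on counts. The varied wording of the hold does not bear on the split. A dedicated unstratified block would also have a price: these 15 patients would not be balanced on 3a/3b, and with an open-label arm the last places in a known block are easier to guess.

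**Conclusion.** The concern is correct as an observation and does not call for a change. The protocol states the make-up of the first cohort without describing how it is secured. Those who build the randomisation schedule fill this gap in the ordinary course of their work.

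If no provision exists and permuted blocks of 15 are used within strata (both assumptions), the exact split would be uncertain: 17% to 0.7% for two-stratum divisions from 14/1 to 8/7. The practical result is usually 2 patients on some dose instead of 3. Even at 8/7, every oral dose has at least one patient in 97% of cases, and a named dose has none in under 1%.

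The cohort is one safeguard among several. Section 10.1.8.2 also has bi-weekly medical monitoring, three early PK evaluations with exposure triggers and the option of more, and referral to a safety committee. Since PK data are related to treatment arm, a short arm could be seen. The primary analysis uses all randomised patients with 3a/3b and country as factors, and is hardly affected. No trial result or conclusion would change.

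A sentence saying that the first 15 patients have their own block, or that the split is an expected count, would be a courtesy to the reader. Any rule for a shortfall is for the sponsor.
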